## APPENDIX C: KARNOFSKY PERFORMANCE STATUS SCALE

### KARNOFSKY PERFORMANCE STATUS SCALE

General	Index	Specific Criteria
Able to carry on normal activity; no special care needed	100	Normal, no complaints, no evidence of disease
	90	Able to carry on normal activity, minor signs or symptoms of disease
	80	Normal activity with effort, some signs or symptoms of disease
Unable to work, able to live at home and care for most personal needs, varying amount of assistance needed	70	Care for self, unable to carry on normal activity or to do work
	60	Requires occasional assistance from others but able to care for most needs
	50	Requires considerable assistance from others and frequent medical care
Unable to care for self, requires institutional or hospital care or equivalent; disease may be rapidly progressing	40	Disabled; requires special care and assistance
	30	Severely disabled, hospitalization indicated, death not imminent
	20	Very sick, hospitalization necessary, active supportive treatment necessary
	10	Moribund
	0	Dead

## APPENDIX D: ECOG Performance Status Scale

### ECOG Performance Status Scale

GRADE	SCALE
0	Fully active, able to carry out all pre-disease performance without restriction
1	Restricted in physically strenuous activity but ambulatory and able to carry out work of a light or sedentary nature, e.g., light housework, office work
2	Ambulatory and capable of all self-care but unable to carry out work activities. Up and about more than 50% of waking hours.
3	Capable of only limited self-care, confined to bed or chair more than 50% of waking hours.
4	Completely disabled. Cannot carry on any self-care. Totally confined to bed or chair.
5	Dead

[figure not shown]
## APPENDIX E: CRS Grading Criteria (CTCAE v. 5.0)

**Definition:** A disorder characterized by fever, tachypnea, headache, tachycardia, hypotension, rash, and/or hypoxia caused by the release of cytokines.

Grade	Description of Symptoms
1: Mild	Fever with or without constitutional symptoms
2: Moderate	Require and respond to moderate intervention: 

• Oxygen requirement < 40%, or

• Hypotension responsive to fluids,

3: Severe	Require and respond to aggressive intervention: 

• Oxygen requirement <math>\geq</math> 40% O2, or

• Hypotension requiring a single vasopressor

4: Life-threatening	Life-threatening; urgent intervention indicated
5: Fatal	Death

a Organ toxicity excludes neurotoxicity, which will be evaluated separately

## APPENDIX F: Recommended Management of CRS

**ASTCT CRS Consensus Grading**

CRS Parameter	Grade 1	Grade 2	Grade 3	Grade 4
Fever*	Temperature $\geq 38^{\circ}\text{C}$	Temperature $\geq 38^{\circ}\text{C}$	Temperature $\geq 38^{\circ}\text{C}$	Temperature $\geq 38^{\circ}\text{C}$
With				
Hypotension	None	Not requiring vasopressors	Requiring a vasopressor with or without vasopressin	Requiring multiple vasopressors (excluding vasopressin)
And/or: †				
Hypoxia	None	Requiring low-flow nasal cannula ‡ or blow-by	Requiring high-flow nasal cannula ‡ , facemask, nonrebreather mask, or Venturi mask	Requiring positive pressure (e.g., CPAP, BiPAP, intubation and mechanical ventilation)

Organ toxicities associated with CRS may be graded according to CTCAE v5.0 but they do not influence CRS grading.

\*Fever is defined as temperature  $\geq 38^{\circ}\text{C}$  not attributable to any other cause. In patients who have CRS then receive antipyretic or anticytokine therapy such as tocilizumab or steroids, fever is no longer required to grade subsequent CRS severity. In this case, CRS grading is driven by hypotension and/or hypoxia.

†CRS grade is determined by the more severe event: hypotension or hypoxia not attributable to any other cause. For example, a patient with temperature of  $39.5^{\circ}\text{C}$ , hypotension requiring 1 vasopressor, and hypoxia requiring low-flow nasal cannula is classified as grade 3 CRS.

‡Low-flow nasal cannula is defined as oxygen delivered at  $\leq 6\text{L}/\text{minute}$ . Low flow also includes blow-by oxygen delivery, sometimes used in pediatrics. High-flow nasal cannula is defined as oxygen delivered at  $> 6\text{L}/\text{minute}$ .

**ASTCT ICANS Consensus Grading for Adults**

Neurotoxicity Domain	Grade 1	Grade 2	Grade 3	Grade 4
ICE Score*	7-9	3-6	0-2	0 (patient is unarousable and unable to perform ICE)
Hypotension	None	Not requiring vasopressors	Requiring a vasopressor with or without vasopressin	Requiring multiple vasopressors (excluding vasopressin)
Depressed Level of Consciousness†	Awakens spontaneously	Awakens to voice	Awakens only to tactile stimulus	Patient is unarousable or requires vigorous or repetitive tactile stimuli to arouse. Stupor or coma.
Seizure	N/A	N/A	Any clinical Seizure, focal or generalized, that resolves rapidly or non-convulsive seizures on EEG that resolve without intervention.	Life-threatening prolonged seizure (>5 min); or repetitive clinical or electrical seizures without return to baseline in between.
Motor Findings‡	N/A	N/A	N/A	Deep focal motor weakness such as hemiparesis or paraparesis
Elevated ICP/Cerebral Edema§	N/A	N/A	Focal/local edema on neuroimaging	Diffuse Cerebral edema on neuroimaging; decerebrate or decorticate posturing; or cranial nerve VI palsy; or papilledema; or Cushing's triad

ICANS grade is determined by the most severe event (ICE score, level of consciousness, seizure, motor findings, raised ICP/cerebral edema) not attributable to any other cause: for example, a patient with an ICE score of 3 who has a generalized seizure is classified as grade 3 ICANS.

N/A indicates not applicable

\* A patient with an ICE score of 0 may be classified as grade 3 ICANS if awake with global aphasia, but a patient with an ICE score of 0 may be classified as grade 4 ICANS if unarousable.

†Depressed level of consciousness should be attributable to no other cause (e.g., No sedating medications)

‡ Tremors and myoclonus associated with immune effector cell therapies may be graded according to CTCAE v5.0, but they do not influence ICANS grading.

§ Intracranial hemorrhage with or without associated edema is not considered a neurotoxicity feature and is excluded from ICANS grading. It may be graded according to CTCAE v 5.0

## APPENDIX G: Long Term Follow-Up

Study participants should be asked to participate in long term follow-up, as directed by the FDA Guidance for Industry – Gene Therapy Clinical Trials: Observing Subjects for Delayed Adverse Events. (<http://www.fda.gov/BiologicsBloodVaccines/GuidanceComplianceRegulatoryInformation/Guidances/CellularandGeneTherapy/ucm072957.htm#5>).

Long term follow-up should commence one year after the final T cell infusion. The planned recommendations for follow-up are as follows:

Years 1 - 15:

1. Recommendation that patients undergo at least annual history and physical examination with their primary physician:
  - Adverse event screening guidance for the primary physician in the form of a gene therapy LTFU-directed screening survey may be available.
  - A request for the study team to be notified of all new malignancies and unexpected illnesses.
  - The primary physician may be provided with a blood draw courier kit to enable samples to be returned to the [name] Lab for archival purposes, and for analysis for transgene and vector persistence, and RCL, as dictated by studies of transferred T cell persistence.
  - If the patient develops a late recurrence, request for up to 50 cc of research blood as well as leftover or archival biopsy/surgical tissue, in order to evaluate for mechanisms of late recurrence (may be collected remotely with a courier kit)
2. Annual phone call survey or questionnaire to the participant to screen for adverse events.
3. Offer the opportunity to return to Fred Hutch for an annual LTFU clinic visit.
4. Compliance with 21 CFR 312.32 in adverse event reporting.
5. Research bloodwork: 30 cc of blood annually for persistence and RCL monitoring

## **APPENDIX H: DOSE ASSESSMENT COMMITTEE**

The Dose Assessment Committee (DAC) will be comprised of investigators directly involved in the study and therefore most knowledgeable regarding balancing safety and efficacy. Members will include:

[name] (Chair)  
[name], PhD (co-Chair)  
[name] [name]  
[name]  
[name] (Biostatistician)

Cellular therapies may not function in dose dependent manner and unique escalation/de-escalation are required to optimally select safe and effective doses. In the event a particular dose is consistently effective or has a substantial number of minor toxicities that do not individually trigger de-escalation, a particular dose in the algorithm may be explored further with additional patients. In such an event, the DAC may override the overall algorithm.

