## 12.0 STATISTICAL CONSIDERATIONS

### 12.1 Type of Study

Our study is a phase I/II, non-blinded interventional trial. Our target sample size is 15-18 patients (8-12 per year/1.5-2 years). This enrollment target is chosen for three reasons: it is achievable from an enrollment standpoint (our clinic sees hundreds of metastatic TNBC, urothelial or NSCLC patients potentially eligible per year), it is logistically possible from a funding and cell processing facility standpoint, and it allows >80% power to observe a statistically significant (at one-sided 0.05 level) efficacy signal that is clinically meaningful (see below). Patients will be treated at three potential dose levels (from  $1 \times 10^9$  up to  $5 \times 10^9$  TCR-MagIC transgenic CD3+).

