### **12.3.2 Definition of success and power of success**

Responses to alternative therapies in this population of patients with advanced TNBC/urothelial carcinoma/NSCLC resistant to PD-1/PD-L1 axis blockade are rare, and we therefore will use a 5% response rate as the fixed benchmark upon which we hope to improve with the proposed treatment. If the true response rate with TCR-transduced cells is 25%, 15 patients yields 84% power to detect a statistically significantly improved response rate (one-sided .05) over the fixed rate of 5%. Three or more responses among 16 pts would occur with probability .04 if the true response rate is 5%, so if three or more patients respond (an observed response rate of at least 19%), we will conclude that this regimen is potentially efficacious and worthy of further study.

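### The three-responder rule in 12.3.2 holds its one-sided 0.05 level only if at most 16 patients are counted, and Appendix H is a second, unsized route past 16

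*Combined protocol and SAP*

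**What the plan says.** Section 12.3.2 fixes the null value: "we therefore will use a 5% response rate as the fixed benchmark". It gives an error rate for one sample size only: "Three or more responses among 16 pts would occur with probability .04 if the true response rate is 5" per cent. The decision rule follows directly: "so if three or more patients respond (an observed response rate of at least 19%), we will conclude" that the regimen merits further study. In the same section, power at a 25% true rate is quoted for a different size: "15 patients yields 84% power to detect a statistically significantly improved response rate (one-sided .05) over the fixed rate of 5" per cent. Section 12.1 claims more than 80% power for a "statistically significant (at one-sided 0.05 level) efficacy signal", and Sections 12.1 and 12.5 both set the target at 15–18 patients over up to three dose levels.

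Appendix H deals with departures from the dose algorithm. "In the event a particular dose is consistently effective", or if it produces many minor toxicities, "a particular dose in the algorithm may be explored further with additional patients", and the committee may override the algorithm to do this. The appendix gives no number of patients and no numerical trigger. Neither it nor Section 12.3 says whether such patients enter the response test.

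**The concern.** The success criterion is a count, and a count holds a given error level only for a given number of patients. The plan names 15, 16 and 15–18 in different places, and Appendix H allows more patients at a dose without saying whether the total grows. If more than 16 patients are counted and three responders still suffice, an inactive regimen is called promising more often than the stated level allows. What is at stake is the claim of significance at one-sided 0.05, and hence how far a positive result supports further development. The trial is non-blinded and the committee is made up of study investigators, so responses will be known when the decision to add patients is taken. The test set should therefore be settled beforehand.

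**Working it through.** **Inputs.** Null rate 5%, alternative 25%, cut-off three responders, N = 16 for the error rate and N = 15 for power (12.3.2); target 15–18 (12.1, 12.5). Section 12.3 does not say whether dose levels are pooled; pooling is assumed here.

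**Step 1: the plan's own figures.** For X ~ Binomial(N, p), P(X ≥ 3) = 1 − P(0) − P(1) − P(2).

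At N = 16, p = 0.05: 1 − 0.4401 − 0.3706 − 0.1463 = 0.0429 (from unrounded terms). This is the stated .04.

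The 84% power at N = 15 is not what the exact rule gives, which is 76.4%. A one-sided normal approximation with null variance and no continuity correction gives 83.2%. That is a separate matter, but it bears on which N to fix.

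**Step 2: the same count at other totals.**

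| N counted | Level at 5% | Power at 25% |
|---|---|---|
| 15 | 0.0362 | 76.4% |
| 16 | 0.0429 | 80.3% |
| 17 | 0.0503 | 83.6% |
| 18 | 0.0581 | 86.5% |
| 20 | 0.0755 | 90.9% |
| 24 | 0.1159 | 96.0% |

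The level is held at 15 and 16, marginally exceeded at 17 and exceeded at 18. None of this needs Appendix H.

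**Step 3: additions prompted by response.** Suppose, as an assumption, that responses are looked at after 16 patients and m more are added if k have responded, with three in total still required:

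level = P(X ≥ 3 | 16) + Σ over triggering k of P(X = k | 16) × P(Y ≥ 3 − k | m), with Y ~ Binomial(m, 0.05).

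- m = 2, added only if k = 2: 0.0429 + 0.1463 × 0.0975 = 0.057. Added if k = 1 or 2: a further 0.3706 × 0.0025, giving 0.058. Fixed N = 18: 0.0581.
- m = 4: 0.070 or 0.075. Fixed N = 20: 0.0755.
- m = 8: 0.092 or 0.113. Fixed N = 24: 0.1159.

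In each case the triggered level is no higher than the level from simply enrolling that total. This is general: success after a triggered addition requires three responders among the patients who would make up the full total, so the fixed-N tail is an upper bound.

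**Step 4: moving patients between doses.** If every dose has a 5% rate and the total is fixed, the pooled count is Binomial(N, 0.05) however patients are allocated. At 18 patients, a simulation with response-dependent allocation gave 0.058, against 0.0581 exact.

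**Step 5: the percentage in parentheses.** 3/16 = 18.75%, which rounds to 19%. Read as a rate rule, it would need four responders from N = 17 (0.19 × 17 = 3.23) to N = 21 (0.19 × 21 = 3.99). The level would then be 0.0088 at 17, 0.0109 at 18 and 0.0189 at 21.

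**The case against.** The strongest reply is that Appendix H is not the source of the excess. Step 3 bears this out: the excess comes entirely from counting more than 16 patients with the cut-off unchanged, and the 15–18 target already allows that. A reader might infer that adding patients because responses look good carries its own penalty on top; with a cumulative count of three it does not.

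Second, the trigger in Appendix H is consistent efficacy at one dose. One or two responders among 16 pooled patients hardly meets that. If the two responders must share a dose (assumed split 6/5/5), the levels for 2, 4, 6 and 8 added patients fall to 0.047, 0.051, 0.054 and 0.057. If three have already responded, the rule is met and additions cannot inflate it. The appendix describes no look at 16, and committee review follows sets of 3 or 4 patients (11.7.4), so exploring a dose further may only mean reallocation within the planned total. The target is also tied to funding and cell-processing capacity. All of this stands, and it is why no single inflation figure can be attached to Appendix H.

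Third, the 19% might be the operative rule, and it would hold the level at 17–21. But the sentence makes the count its condition, and the percentage matches 3/16 only after rounding up. At best the wording is ambiguous and needs settling.

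Fourth, a positive result leads only to further study, and Sections 12.3–12.4 plan no dose-specific response estimate. That limits the consequence, and it means a claim of upward bias at an expanded dose concerns an analysis the plan does not specify.

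**Conclusion.** The stated one-sided 0.05 level is guaranteed only if at most 16 patients are counted. Within the planned range it reaches 0.0503 at 17 and 0.058 at 18. Appendix H is a second route past 16, because it sets no number and does not say whether the added patients count. If the total grew to 20 or 24, the level would be at most 0.0755 or 0.116. The size, timing and trigger of any addition are assumptions, and so is pooling across doses.

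Two stronger readings are tempting. One is that the 0.05 level is simply not held: at 15 or 16 patients, the second being the number the rule names, it is. The other is that the protocol defines no test set anywhere: the text available begins within Section 10 and Figure 6 is not shown, so this can be said only of the sections from there on. Those do include all of Section 12 and Appendix H, where such a definition would be expected. The point is moderate in size, but it affects the trial's one formal efficacy decision and is easily closed.

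**What to change.** In 12.3.2, state that the success test uses the first 16 infused patients in order of first infusion, at whatever dose and whether or not they were treated under Appendix H. The level is then 0.043 and the exact power at 25% is 80.3%, which agrees with the more than 80% claimed in 12.1. Patients infused after the 16th, including any Appendix H additions, are reported separately by dose with exact confidence intervals and do not count toward the three. Add a cross-reference in Appendix H.

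Defining the set by infusion order alone matters: a patient added under Appendix H as, say, the eighth infused stays in the test, so the denominator remains 16. If enrolment closes at 15, the level is still held (0.0362), with power of 76.4%.

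The cost is one sentence and a cross-reference. The committee's discretion is untouched. The downside is that patients after the 16th, including planned patients 17 and 18, do not contribute to the formal test. The alternative is a cut-off stated for each total, which is four responders for N = 17–28. It also holds the level, but power at 25% falls to 64.7% at 17 and 69.4% at 18, and does not pass 80% again until 21 patients (80.8%).

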## **APPENDIX I: MAGE-A1-SPECIFIC IMMUNOHISTOCHEMISTRY (IHC) ASSAY**

### **1. Description of the assay**

The MAGE-A1 selection assay is a standard single-color chromogenic immunohistochemistry assay developed for use on formalin-fixed paraffin-embedded tissue. Monoclonal antibody MA454 is specific to MAGE-A1 and is detected with an anti-mouse polymer conjugated to horse radish peroxidase. DAB chromogen creates a brown pigment visible using standard brightfield microscopy. Results are provided via interpretation by a board-certified pathologist.

### **2. Application of assay results to the clinical trial**

MAGE-A1-specific IHC will be used as one of the subject eligibility criteria for treatment with engineered autologous T cell therapy, FH-MagIC TCR-T. FH-MagIC TCR-T is specific to a Class I HLA A\*0201-restricted MAGE-A1 epitope. The rationale is that the engineered autologous T cell product will target tumor cells with MAGE-A1 antigen to be present before TCR will be able to deliver immunomodulating therapeutic effects.

A positive MAGE-A1 IHC result is required for enrollment. A positive result is any tumor with >10%, 1+ or higher staining intensity, membranous, nuclear or cytoplasmic expression of MAGE-A1.

### **3. Description of the population and information regarding what is known about the prevalence of the biomarker being evaluated in the patient population**

MAGE-A1 plays a role in transcriptional control of cancers and have been shown to inhibit the activity of tumor suppressor microRNA Let7a. Overexpression of this protein has been noted in multiple solid tumors and have become an attractive therapeutic target. The MAGE-A1 IHC assay detects expression of MAGE-A1 protein on cells in the tumor tissue, a pathologist will interpret if the expression of the protein is seen in tumor cells, stromal cells, or inflammatory cells and if the protein is likely membranous, cytoplasmic, and or nuclear.

### **4. Specimen type(s) to be collected for investigational IVD testing, including the anatomical site**

MAGE-A1 IHC selection assay will be performed on archival FFPE tumor specimens. Biopsies will not be conducted exclusively for patient selection testing.

### **5. Risk Analysis**

Aside from immune-privileged testes, MAGE-A1 is undetectable in most normal tissues. MAGE-A1 IHC shows 93% specificity, 69% sensitivity, and 100% precision (reproducibility) when calculated from the validation sample set. This represents a low likelihood of false positive test results, and a 31% possibility of false negative results. Since this assay will be used for patient

selection in a safety phase clinical trial with unknown efficacy, there is minimal risk associated with a false negative test result.
